## 1. Purpose/Specific Aims

This study aims to determine the average level of physical activity using average step counts and daily MET  $\text{min}^{-1}$  following vaginal and cesarean delivery through use of Actigraph GT3X (a fitness tracker).

### *1.1 Objectives*

The main objective of the study is to determine the average level of physical activity using mean daily steps and daily MET  $\text{min}^{-1}$ , in women post vaginal and cesarean delivery.

### *1.2 Hypotheses*

The Actigraph GT3X will determine physical activity and step counts and these will be greater in women following vaginal delivery compared to cesarean delivery in a 48 hour period.

## 2. Background and Significance

Cesarean delivery is the most common surgery performed in the United States. Despite this fact, there is a paucity of literature looking into the implementation of enhanced recovery after surgery (ERAS) for patients undergoing this type of surgery. ERAS protocols have shown to improve recovery from surgery, decreasing complication and hospital length of stay. The pathway for enhanced recovery targets improving factors that have been associated with increased hospital length of stay and complications. These factors are pain, immobilization and postoperative ileus. These factors, many times are inter-related. A patient in pain would tend not to ambulate as this may exacerbate the pain and discomfort. In order to alleviate pain, the patient would most likely receive an opioid for pain management and these medications are known to have undesirable side effects such as nausea, vomiting, sedation, respiratory depression, constipation and urinary retention. All of these adverse effects (AEs) may lead to complications or increased hospital length of stay.

To the best of our knowledge the average level of physical activity (PA) of parturients recovering from a cesarean delivery or after a normal spontaneous vaginal delivery (NSVD) remains unknown. Taking in consideration that parturients are in a hypercoagulable state and that obstetric venous thromboembolism (VT) is one of the most common causes of maternal morbidity and mortality, ambulation is of utmost importance to anesthesiologists as well as obstetricians. In order to promote mobility, first we need to learn the average parturients level of physical actity in the immediate post-partum period and up to 48 hours after delivery. This information may help us promote mobility in the immediate postpartum period, particularly for those that underwent a cesarean delivery since they are at higher risk of VT.

Given the lack of knowledge regarding the physical activity level of parturients in the postpartum period we have designed a pilot study to objectively measure their PA. Patients having a normal spontaneous vaginal delivery will serve as our control group. These patients are going through the same physiologic changes that their counterparts (CD patients) are going through, the only difference being the stress of surgery in the CD group. The use of Fitness trackers (i.e Fitbit(R), Actigraph GT3X +) has been used to measure and promote physical activity in a cardiac rehabilitation population, as well as in parturients self-identified as inactive. We intend to use the Actigraph GT3X+ to measure the level of physical activity of 50 parturients (25 NSVD and 25 post CD). The information obtained, we expect, will help us tailor the anesthetic/analgesic management of parturients in such a way that promotes early ambulation and recovery. We estimate that we need approximately a total of 50 patients, 25 per group to assess if there is a difference in the level of PA between parturients after a NSVD or CD. We will aim to recruit 60 patients per group to account for missing data, protocol violations, equipment malfunction or patients drop outs.

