### ***3.3 Sample Size Justification***

This study has been designed as a pilot study. Sixty subjects will be enrolled to account for subject withdrawal, lost data, protocol violation. The investigators plan to analyze 50 subjects (25/per group ).

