### **4. Data Handling and Statistical Analysis**

The study data will be collected on the data collection form. Subjects will be assigned a code consisting of a number and letters designating the mode of delivery, the first subject at Rutgers

New Jersey Medical School 1RNJMS-CD or 1RNJMS-NSVD). The first page of the data collection form, which contains limited protected health information (patient name, MRN) will be kept until all data is gathered, then the form will be de-identified by destroying the first page, saving only the subject number. All forms will be securely kept in a locked cabinet in the locked office of the principal investigator at each participating institution. All digital data stored on computers will be on encrypted drives. Only study team participants will have access to the collected data.

There are no specific privacy issues beyond the confidentiality of study data as described above.

This will be a pilot prospective study, in which objective physical activity (measured as mean daily steps and daily MET min) will be the main primary outcome. Given that this is a pilot study, we estimate that we need approximately a total of 50 patients, 25 per group to assess if there is a difference in the level of PA between parturients after a NSVD or CD. We will aim to recruit 60 patients total to account for missing data, protocol violations, equipment malfunction or patients drop outs.

ANOVA will be used to study variability between groups. Kruskal Wallis will be used for averages.

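### The enrolment target is 60 women per group (120 in all) in the Background but 60 in total in the statistical section, for the same 50 analysed

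*Combined protocol and SAP*

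**What the plan says.** Three places in the combined protocol and SAP give an enrolment target.

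- **Section 2, Background and Significance (last paragraph):** "We will aim to recruit 60 patients per group to account for missing data".
- **Section 3.3, Sample Size Justification:** "Sixty subjects will be enrolled to account for subject withdrawal, lost data, protocol violation".
- **Section 4, Data Handling and Statistical Analysis** (the second section numbered 4): "We will aim to recruit 60 patients total to account for missing data, protocol violations, equipment malfunction or patients drop outs".

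The number needed or analysed is the same in all three. Section 2 says "We estimate that we need approximately a total of 50 patients, 25 per group" and also plans to "measure the level of physical activity of 50 parturients (25 NSVD and 25 post CD"). Section 3.3 says "The investigators plan to analyze 50 subjects (25/per group"). The statistical section again gives 50, as 25 per group.

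Section 3 (Research Design and Methods) describes a multicenter study with two groups defined by mode of delivery. Section 3.1 gives a study duration of one year. The text available for review states no loss rate and no enrolled number for each mode of delivery.

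**The concern.** The sentences in section 2 and in the statistical section match except that one sets the 60 per group and the other sets it in total. With two groups, the first means 120 women and the second 60. Since the analysed number is fixed at 50, the extra recruits can only be an allowance for loss, and one allowance cannot be both 10 women and 70.

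Three things are at stake:

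- **Number of women approached.** Consent is sought within hours of delivery (sections 3.5.3 and 3.5.4). The two readings differ by 60 women.
- **When recruitment stops.** In a multicenter study, sites reading different sections could work to different totals.
- **What happens to surplus data.** Under the 120 reading, more than 50 women would have usable data unless loss reached 58.3%. The plan does not say whether data beyond 25 per group would be analysed, so women could be selected for analysis after their data are known.

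**Working it through.** **Inputs**

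| Quantity | Value | Source |
|---|---|---|
| Number analysed | 50 (25 + 25) | Sections 2, 3.3 and Data Handling and Statistical Analysis |
| Enrolment, reading A | 60 per group | Section 2 |
| Enrolment, reading B | 60 total | Data Handling and Statistical Analysis; section 3.3 read as a total |
| Number of groups | 2 | Section 3 |
| Study duration | 12 months | Section 3.1 |
| Loss rate | Not stated | – |

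**Can the plan's figures be reproduced?** The 50 cannot be, because no significance level, power, effect size or standard deviation is given. The enrolment target cannot be derived directly either, because no loss rate is given. What can be tested is whether either target is a plausible inflation of 50.

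**Section 3.3.** It attaches no group label to its sixty, yet its next sentence does label 25 as a group figure. The sixty therefore reads as a total.

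**Implied loss, d = 1 − 50/N**

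- Reading A: N = 60 × 2 = 120; d = 1 − 50/120 = 70/120 = 58.3%; inflation 120/50 = 2.4.
- Reading B: N = 60; d = 1 − 50/60 = 10/60 = 16.7%; inflation 60/50 = 1.2.

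**Working forwards, N = 50/(1 − d), rounded up, with assumed d**

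| Assumed loss | Enrolment needed |
|---|---|
| 10% | 56 |
| 15% | 59 |
| 16.7% | 60 |
| 20% | 63 |
| 58.3% | 120 |

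The cruder form N = 50 × (1 + d) gives exactly 60 at d = 20%, and needs d = 140% to reach 120. A total of 60 therefore fits a loss of about 15% to 20%. Neither formula reaches 120 with a loss in that range, and neither reconciles the two targets.

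**Usable women, N × (1 − d), with assumed d**

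| Assumed loss | From 60 | From 120 | Surplus over 50, from 120 |
|---|---|---|---|
| 10% | 54 | 108 | 58 |
| 16.7% | 50 | 100 | 50 |
| 20% | 48 | 96 | 46 |
| 30% | 42 | 84 | 34 |

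**Accrual.** If the whole year were used for enrolment, the average would be 60/12 = 5 women per month under B and 120/12 = 10 under A.

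**The case against.** The best reply is that the documents nearly settle the matter themselves. The sample size section and the statistical section, where an enrolment target belongs, both give 60, and the outlier is one phrase in the Background. That same paragraph plans to measure 50 women, for which 60 is a plausible allowance and 120 is not. The planned analysis is unchanged and the study is observational. The only harm foreseen is a mild skin reaction (section 4.3). On this view the error is administrative: an inconsistency of wording rather than a faulty calculation.

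Much of this stands. A slip in section 2 is the likeliest explanation, and no calculation in the plan has been shown to be wrong. The accrual figures show no feasibility problem, since section 3.1 gives a study duration rather than an enrolment window and the number of sites is not visible. The surplus figures rest on an assumed loss range. The missing loss rate, the unstated split and the handling of surplus data would also remain after the phrase was corrected: 60 enrolled at 10% loss already leaves 54. A rule to analyse every woman with usable data goes beyond the plan's stated 50, and would need a definition of usable wear data.

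None of this removes the contradiction. The enrolment target is an operating figure, and anyone relying on section 2 alone would recruit to twice the number. Some front matter and the text between sections 3.1 and 3.3 were not available for this check, but nothing there could make the two sentences agree.

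**Conclusion.** The concern holds and should be fixed. The current text sets two incompatible enrolment targets, 60 and 120, for the same 50 women analysed. The implied loss is 16.7% under one and 58.3% under the other, with inflation of 1.2 and 2.4 times.

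These figures follow directly from the plan and need no outside assumption beyond reading section 3.3's sixty as a total. Without section 3.3, the conflict between section 2 and the statistical section still stands. The surplus of 34 to 58 women under the larger target depends on an assumed loss of 30% to 10%, and the accrual rates depend on using the full year for enrolment. They illustrate the consequence and are not needed for the conclusion.

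The weight of the text favours 60 in total, but only the sponsor can confirm it. The error lies in enrolment and in the allowance for loss, not in the 25 v 25 comparison.

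**What to change.** 1. The sponsor confirms the approved enrolment number. If it is 60, section 2 is changed to give 60 as the total, matching section 3.3 and the statistical section. If it is not 60, all three places are aligned to the approved figure.
2. State the intended split by mode of delivery. With 60 enrolled and equal groups this would be 30 each, which is an inference from the 25/25 analysed and is not in the documents.
3. State the loss rate assumed. The implied rate for 60 is 16.7%, and a higher loss would leave fewer than 50.
4. State how usable data beyond 25 per group are handled. The recommended rule is to analyse all enrolled women with usable wear data, with usable defined in advance, so that nobody is dropped merely to reach 25.

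Item 1 resolves the contradiction. Items 2 to 4 close related gaps that would otherwise remain. If 60 is confirmed, the cost is one phrase in section 2 and a few clarifying sentences, with no extra patients.

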### **3. Research Design and Methods**

This will be a multicenter pilot, prospective study aimed at measuring the physical activity (PA) of American Society of Anesthesiologists (ASA) Classification I and II women aged 18 years and older, after a normal spontaneous vaginal (NSVD) or cesarean delivery (CD). Subjects will be ASA I and II women aged 18 years and older, knowing to have had either a NSVD or CD (under neuraxial anesthesia). After delivery, and assuring that mother and baby are stable, patients will be approached by a member of the study team to discuss the study and obtain informed consent. After obtaining informed consent, patients will be divided into Two (2) groups depending on the mode of delivery. Group 1 will be NSVD and group 2 will be CD patients. Patients will be provided with a fitbit- based Actigraph GT3X + hardware, 6 hours after delivery. Patients will be evaluated every 12 hours after delivery for a period of 48 hours. During these evaluation points, pain (visual analogue scores), factors affecting mobility, and level of satisfaction with their analgesia will be assessed. After 48 hrs the Actigraph GT3X + will be interrogated and objective data, such as mean daily steps and daily MET min, will be obtained using the aforementioned software.

#### ***3.1. Duration of Study***

One year

### ***3.3 Sample Size Justification***

This study has been designed as a pilot study. Sixty subjects will be enrolled to account for subject withdrawal, lost data, protocol violation. The investigators plan to analyze 50 subjects (25/per group ).

### ***3.4 Subject Selection and Enrollment Considerations***

The study subjects will be American Society of Anesthesiologists (ASA) classification I and II women aged 18 years and older, knowing to have had either a NSVD or CD using a neuraxial analgesia/anesthesia technique.

#### ***3.5.1 Inclusion Criteria***

The study subjects will be ASA I and II women aged 18 years and older, knowing to have had either a NSVD or CD using a neuraxial analgesia/anesthesia technique.

#### ***3.5.2 Exclusion Criteria***

History of chronic pain  
Recent use of opioids (other than postpartum)  
Emergency case requiring general anesthesia (GA) or conversion to GA  
BMI > 45  
Need to perform more extensive surgery (i.e Hysterectomy)  
Need for the neonate to be admitted to NICU (This will prompt mothers to walk more frequently, and longer distances to visit the baby)

#### ***3.5.3 Subject Recruitment***

Patients will be recruited after a known NSVD or CD. Patients will be approached after assuring that both the parturient and the neonate are stable. The patient will be recruited within the first 6 hrs after delivery.

#### ***3.5.4 Consent Procedures***

Informed consent will be obtained by one of the investigators after assuring maternal and fetal wellbeing. The parturient will be approached within the first two to six hours after delivery. A thorough explanation of the protocol will be given by one of the investigators.

#### ***3.5.5 Subject Costs and Compensation***

Subjects will not be compensated for their participation in the study.

### ***3.6 Chart Review Selection***

The study data will be collected from the subject as well as a review of the subjects Medication Administration documents found in EPIC.

## **4. Study Variables**

#### **4.1 Independent Variables or Interventions**

*Independent variables:* Demographic and labor data (patient age, ethnicity, height, weight, body mass index (BMI), gravity, parity, time of delivery, mode of anesthesia or analgesia, mode of delivery, post-partum analgesia (iv or po analgesia), number of previous CD and prior abdominal surgery).

*Interventions:* After obtaining informed consent, patients will be assigned to either the NSVD or CD group. Patients will be provided with a fitbit- based Actigraph GT3X + hardware, 6 hours after delivery. Physical activity will be objectively measured using the Actilife software and fitbit- based Actigraph GT3X + hardware. Physical activity will be measured as mean daily steps and daily MET min. This data will be obtained at 48 hours after NSVD or CD and will be compared at the 12 hour, 24 hour, 36 hour, and 48 hour time points.

##### **4.1.1 Drug or Device Interventions**

The Actigraph GT3X-BT (Actigraph, Florida, US) is an accelerometer that assesses total body displacement across a vertical plane and determines physical activity levels in the form of activity and step counts. This device has been previously validated.

#### **4.2 Dependent Variables or Outcome Measures**

*Dependent variables:* Factors contributing to immobility (i.e foley catheter), pain scores at rest and with movement will be measured using VAS scores, medications administered and satisfaction with analgesia will be monitored every 12 h for 48 h.

##### *Outcome measures:*

Primary: mean average steps and MET min

Secondary: Pain and satisfaction scores

#### **4.3 Risk of Harm**

This study does not involve any potential risk to the patient. The patients will simply be asked to wear a wrist fitbit-based accelerometer (Actigraph GT3X-BT). At most, it is possible that some patients may develop a rash or mild skin reaction to the wrist band of the aforementioned device.

#### **4.4 Potential for Benefit**

The potential benefit from participating in this study includes helping physician to gain knowledge as to the physical activity of parturients immediately postpartum. The knowledge gained may help us tailor our analgesic strategies or simply encourage the parturient to increase their physical activity, particularly after CD as those patients are at higher risk for thromboembolic events.

### **4. Data Handling and Statistical Analysis**

The study data will be collected on the data collection form. Subjects will be assigned a code consisting of a number and letters designating the mode of delivery, the first subject at Rutgers

New Jersey Medical School 1RNJMS-CD or 1RNJMS-NSVD). The first page of the data collection form, which contains limited protected health information (patient name, MRN) will be kept until all data is gathered, then the form will be de-identified by destroying the first page, saving only the subject number. All forms will be securely kept in a locked cabinet in the locked office of the principal investigator at each participating institution. All digital data stored on computers will be on encrypted drives. Only study team participants will have access to the collected data.

There are no specific privacy issues beyond the confidentiality of study data as described above.

This will be a pilot prospective study, in which objective physical activity (measured as mean daily steps and daily MET min) will be the main primary outcome. Given that this is a pilot study, we estimate that we need approximately a total of 50 patients, 25 per group to assess if there is a difference in the level of PA between parturients after a NSVD or CD. We will aim to recruit 60 patients total to account for missing data, protocol violations, equipment malfunction or patients drop outs.

ANOVA will be used to study variability between groups. Kruskal Wallis will be used for averages.

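### The vaginal versus cesarean comparison has no pre-specified adjustment for baseline differences or site, although the data needed are already collected

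*Combined protocol and SAP*

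**What the plan says.** The plan has a descriptive and a comparative aim. Section 1.1 is descriptive: "The main objective of the study is to determine the average level of physical activity" after each mode of delivery. Section 1.2 is comparative. It predicts of activity and step counts that "these will be greater in women following vaginal delivery compared to cesarean delivery in a 48 hour period". Section 4 (Data Handling and Statistical Analysis) ties the 25 per group to this second aim: "to assess if there is a difference in the level of PA between parturients after a NSVD or CD".

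The methods named in that section are "ANOVA will be used to study variability between groups. Kruskal Wallis will be used for averages". No covariate, site term, regression, stratification or matching appears there or elsewhere in the public text.

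On design, section 3 states "This will be a multicenter pilot, prospective study" and that "patients will be divided into Two (2) groups depending on the mode of delivery". Section 4.1 lists age, BMI, parity and time of delivery among the independent variables but links them to no model. Sections 3.5.1 and 3.5.2 restrict entry: ASA I-II, a neuraxial technique, BMI not above 45, and no NICU admission of the neonate, among others. Section 2 presents vaginal delivery as the control condition, "the only difference being the stress of surgery in the CD group".

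**The concern.** Mode of delivery is not assigned by the study, so the groups can differ in baseline factors that also affect walking. The protocol accepts that such factors exist: it excludes mothers of neonates admitted to NICU because visits would change how much they walk. Within the eligibility limits, age, parity, BMI up to 45, site and hour of delivery can still differ between groups. A test without these terms estimates mode of delivery mixed with whatever differs, while section 2 encourages the reader to put the whole difference down to surgery.

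Hour of delivery deserves separate attention because the design itself creates the problem. Section 3 says "Patients will be provided with a fitbit- based Actigraph GT3X + hardware, 6 hours after delivery", and the data are read at 48 h. The window lasts 42 h, which is not a whole number of days, so the daytime it contains depends on the clock hour of delivery.

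**Working it through.** **Text check.** Non-random groups, several sites, covariates recorded, and an analysis section that names two tests and no covariate: each is stated in the sections cited above. The documents give no alpha, power, SD or effect size, so the 25 per group cannot be reproduced. With an assumed two-sided 5% level, 25 versus 25 has 80% power for 0.81 SD (t-based; 0.79 SD by the normal approximation).

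**Hour of delivery: illustration.** From the documents: device provided at 6 h, read at 48 h, comparisons at 12, 24, 36 and 48 h. Assumed: night 22:00-06:00, steps proportional to daytime hours, NSVD even over the clock, a share *s* of CDs even over 06:00-16:00 and the rest even over the other 14 h.

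1. Any 48 h span holds 32 daytime hours. The 6-48 h window holds 32 minus those in the first 6 h: range 26 to 32, mean 28 for NSVD.
2. For delivery at 06:00-16:00 the first 6 h are all daytime, so the window holds 32 - 6 = 26. For the other 14 h the mean is (24×28 - 10×26)/14 = 29.43.
3. Spurious NSVD excess with no effect of mode: *s* = 0.5 gives a CD mean of 27.71, and 28/27.71 - 1 = 1.0%. *s* = 1 gives 28/26 - 1 = 7.7%. *s* = 10/24 = 41.7% gives zero; below that the sign reverses.
4. If the night step rate is a fraction *r* of the day rate, at *s* = 1 the excess is (28 + 14*r*)/(26 + 16*r*) - 1: 5.0% for *r* = 0.25 and 2.9% for *r* = 0.5. At *s* = 0.5 and *r* = 0.5 it is 35/34.86 - 1 = 0.4%.
5. In SD units (excess divided by an assumed coefficient of variation of 50% to 100%), 1.0% to 7.7% is 0.01 to 0.15 SD. The two-sided false-positive rate at 25 versus 25 is then 5.0% to 8.3%.

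**The 12-hourly comparisons.** Section 4.1 does not say whether values are per interval or cumulative. Mean daytime hours under the same assumptions, with no night steps:

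| Period | NSVD | CD, *s* = 0.5 | CD, *s* = 1 | NSVD excess |
|---|---|---|---|---|
| 6-12 h | 4 | 4.03 | 4.2 | -0.7% to -4.8% |
| 12-24 h | 8 | 7.69 | 5.8 | +4.1% to +37.9% |
| 24-36 h | 8 | 8.31 | 10.2 | -3.8% to -21.6% |
| 36-48 h | 8 | 7.69 | 5.8 | +4.1% to +37.9% |
| Cumulative to 24 h | 12 | 11.71 | 10.0 | +2.4% to +20.0% |
| Cumulative to 36 h | 20 | 20.03 | 20.2 | -0.1% to -1.0% |
| Cumulative to 48 h | 28 | 27.71 | 26.0 | +1.0% to +7.7% |

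With *r* = 0.5 the 12-24 and 36-48 h range shrinks to +1.6% to +12.4%, and the 24-36 h range to -1.5% to -9.9%.

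**Other covariates.** Nothing in the documents sizes these. For one generic covariate with an assumed group imbalance of 0.5 SD and an assumed correlation of 0.3 with the outcome, the bias is 0.3×0.5 = 0.15 SD. In a simulation with no true effect, the false-positive rates were 8.5% (ANOVA), 8.3% (Kruskal-Wallis) and 5.4% (adjusted). At correlation 0.5 they were 13.7%, 13.3% and 5.0%. With no imbalance all are about 5%.

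**Price of adjusting.** Intercept, mode and four covariates make 6 parameters, plus sites minus 1. The number of sites is not visible in the public text; an assumed 2 to 5 gives 7 to 10 parameters and leaves 43 to 40 df from 50 women (critical t 2.017 to 2.021, against 2.011 unadjusted). Four independent covariates, each imbalanced by an assumed 0.5 SD, explain 0.25/1.25 = 0.20 of group membership. If they explain 0.1 to 0.3 of the outcome variance (assumed), the standard error changes by √(0.9/0.8) = 1.06 to √(0.7/0.8) = 0.94, before any site imbalance.

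**The case against.** This is a pilot whose main objective is to describe averages, and eligibility already removes some confounding. ANOVA can carry covariates and the plan does not rule them out. For the 48 h outcome the one bias that can be traced to the design is small, and its top value needs every CD in daytime hours and no steps at night. For age, BMI, parity and site, no imbalance or link to steps is documented. The sentence in section 2 can be read as background on physiology, not as an analysis assumption.

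Most of this stands, and it limits the weight of the point. It does not remove it: the plan also states a directional hypothesis and bases its group size on a comparison, and listing variables as independent does not specify a model.

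A reader might infer that all four time-point comparisons are more exposed than the 48 h total. The table does not support that. The 6-12 h interval and the cumulative 36 h value are less affected, and the cumulative 48 h value is the primary window itself. Nor can a false recovery pattern be asserted: the material change of sign occurs only if values are per interval, which the protocol leaves open.

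**Conclusion.** The concern holds for the comparative aim and not for the descriptive one. As written, the comparison carries no control for baseline differences beyond eligibility, and the design does not assure that surgery is the only difference between groups.

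The size is unknown. For hour of delivery alone, under the stated assumptions, the 48 h outcome is biased by 1.0% to 7.7%, or 0.4% to 2.9% with a night step rate half the day rate: little beside a detectable difference of 0.81 SD. Larger values arise only at 12-24, 24-36 and 36-48 h if values are per interval, or at 24 h if they are cumulative. A reader might take the 38% or the simulated error rates as an estimate of the bias in this study; they are outcomes of assumed inputs. The case rests on the absence of any pre-specified adjustment, which should be remedied, and not on one scenario. Confidence is medium.

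**What to change.** In section 4 (Data Handling and Statistical Analysis), keep the unadjusted comparison and the per-group averages. Beside them, pre-specify one supportive linear model for mean daily steps and one for MET min, each on mode of delivery and adjusted for:

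- age and BMI;
- parity before the index birth (0 versus 1 or more), with the counting rule stated because women are recruited after delivery;
- daytime hours in the wear window, derived from the recorded time of delivery, with the clock cut fixed in advance (06:00-22:00 above is only an assumption);
- site.

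Do not adjust for pain, postpartum analgesia or foley catheter: these follow delivery and may lie on the path from mode of delivery to activity. In section 2, replace the claim of a single difference with a statement that the comparison is observational and residual confounding remains.

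The cost is wording only. Section 4.1 already collects the covariates and the subject code carries the site. The model uses 4 df plus sites minus 1 from about 50 women, and the standard error may be roughly 6% wider to 6% narrower under the assumptions above, before any site imbalance. No gain in precision should be claimed. How the time-point values are defined, repeated measures on the same woman and the choice of outcome scale are separate matters.
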